3.9 Discontinuation from study treatment

If a subject's study treatment must be discontinued, this will not result in automatic withdrawal of the subject from the study. If a subject discontinues study treatment for any reason before the end of the treatment phase, end-of-treatment assessments should be obtained and scheduled follow-up phase assessments should continued as specified in the Time and Events Schedule.

Patients may be discontinued from the study drug treatment in the following situations:

- The subject experiences disease progression (as per participating physician's assessment)
- Adverse Event (including laboratory abnormality or intercurrent illness) which, in the opinion of the investigator, indicates that continued participation in the study is not in the best interest of the patient
- The subject (or the subject's legally acceptable representative) withdraws consent for administration of study drug
- The subject received concurrent (non-protocol) anti-cancer treatment for NSCLC
- ILD/Pneumonitis
- Corneal ulcerations
- QTc interval prolongation with signs/symptoms of serious arrhythmia
- Pregnancy
- Any adverse event deemed to be related to osimertinib that requires a dose hold of more than 21 days will result in permanent discontinuation of osimertinib.
- Grade 3 or higher adverse reaction that does not improve to Grade 0-2 after withholding for up to 3 weeks

The primary reason for discontinuation of study treatment is to be recorded in the eCRF.

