3.9.1 Procedures for discontinuation of a patient from study drug

At any time, patients are free to discontinue study drug or withdraw from the study (i.e., study drug and assessments), without prejudice to further treatment. A patient that decides to discontinue study drug will always be asked about the reason(s) and the presence of any adverse events. If possible, they will be seen and assessed by an Investigator(s). Adverse events will be followed up (See Section 6) and all study drugs should be returned by the patient.

Enrolled patients who discontinue the study prematurely should immediately stop taking study drug and complete the procedures described for End of Treatment Visit, as soon as possible but not later than 7 days after discontinuation of study drug.

If a patient is withdrawn from study, see Section 3.9, 3.10, 3.11.

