3.10 Criteria for withdrawal

3.10.1 Withdrawal of the informed consent

Patients are free to withdraw from the study at any time (study drug and assessments), without prejudice to further treatment.

Reasons for withdrawal from the study:

- Eligibility criteria not fulfilled
- Death
- Withdrawal of consent.
- Lost to follow up (unsuccessful contact with patient despite every effort made by investigator)

Patients who withdraw consent for further participation in the study will not receive any further study drug or further study observation. Note that the patient may be offered additional tests to withdraw safely.

A patient who withdraws consent will always be asked about the reason(s) and the presence of any adverse events (AE). The Investigator will follow up AEs outside of the clinical study. If a patient withdraws from participation in the study, then his/her enrolment code cannot be reused. Withdrawn patients will not be replaced.

Patients will be considered lost to follow-up only if no contact has been established by the time the study is completed, such that there is insufficient information to determine the patient's status at that time. Patients who refuse continuing participation in the study, including telephone contact, should be documented as "withdrawal of consent" rather than "lost to follow-up." Investigators should document attempts to re-establish contact with missing patients throughout the study period. If contact with a missing patient is re-established, the patient should not be considered lost to follow-up and any evaluations should resume according to the protocol.

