6.7 Management of study drug related toxicities

If a patient experiences a CTCAE grade 3 and/or unacceptable toxicity not attributable to the disease or disease-related processes under investigation, dosing will be interrupted and supportive therapy administered as required in accordance with local practice/guidelines.

If a toxicity resolves or reverts to ≤CTCAE grade 2 within 3 weeks of onset, treatment with study drug may be restarted at the same dose (80 mg) or a lower dose (40 mg) using the rules below for dose modifications (Table 3) and with discussion and agreement with the AstraZeneca Study Team Physician as needed. There will be no individual modifications to dosing schedule in response to toxicity, only potential dose reduction or dose interruption.

If the toxicity does not resolve to ≤CTCAE grade 2 after 3 weeks, then the patient should be withdrawn from the study and observed until resolution of the toxicity.

Table 3. OSIMERTINIB dose adjustment information for adverse reactions

Target		
organ	Adverse reaction ^a	Dose modification
Pulmonary	ILD/Pneumonitis	Permanently discontinue OSIMERTINIB
Cardiac	QTc interval greater than 500 msec on at least 2 separate ECGs	Withhold OSIMERTINIB until QTc interval is less than 481 msec or recovery to baseline if baseline QTc is greater than or equal to 481 msec, then restart at a reduced dose (40 mg)
	QTc interval prolongation with signs/symptoms of serious arrhythmia	Permanently discontinue OSIMERTINIB
Other	Grade 3 or higher adverse reaction	Withhold OSIMERTINIB for up to 3 weeks
	If Grade 3 or higher adverse reaction improves to Grade 0-2 after withholding of OSIMERTINIB for up to 3 weeks	OSIMERTINIB may be restarted at the same dose (80 mg) or a lower dose (40 mg)
	Grade 3 or higher adverse reaction that does not improve to Grade 0-2 after withholding for up to 3 weeks	Permanently discontinue OSIMERTINIB

^a Note: The intensity of clinical adverse events graded by the National Cancer Institute (NCI) Common Terminology Criteria for Adverse Events (CTCAE) version 4.0.

ECGs: Electrocardiograms; QTc: QT interval corrected for heart rate

On resolution of toxicity within 3 weeks:

• If an AE subsequently requires dose interruption, study drug may restart at the same dose or the reduced dose, on resolution/improvement of the AE at the discretion of the Investigator.

ILD/Pneumonitis-like toxicity

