If new or worsening pulmonary symptoms (e.g., dyspnoea) or radiological abnormality suggestive of interstitial lung disease is observed, an interruption in study treatment dosing is recommended, and the AstraZeneca study team should be informed. It is strongly recommended to perform a full diagnostic workup, to exclude alternative causes such as lymphangitic carcinomatosis, infection, allergy, cardiogenic edema, or pulmonary hemorrhage. The results of the full diagnostic workup (including high-resolution computed tomography, blood and sputum culture, haematological parameters) will be recorded in the CRF by the investigator. In the presence of confirmatory HRCT scans where other causes of respiratory symptoms have been excluded, a diagnosis of interstitial lung disease (ILD) should be considered and study treatment permanently discontinued.

In the absence of a diagnosis of ILD study treatment may be restarted following consultation with the AstraZeneca Study Team Physician.

QTc prolongation

Patients with QTcF prolongation to >500 msec should have study treatment interrupted and regular ECGs performed until resolution to <481 msec or recovery to baseline if baseline QTcF is >481 msec and then restarted at a reduced dose of 40 mg. If the toxicity does not resolve to ≤grade 1 within 21 days the patient will be permanently withdrawn from study treatment.

Keratitis

Patients presenting with signs and symptoms suggestive of keratitis such as acute or worsening: eye inflammation, lacrimation, light sensitivity, blurred vision, eye pain and/or red eye should be referred promptly to an ophthalmology specialist.

Changes in cardiac contractility

In patients with cardiac risk factors and those with conditions that can affect LVEF, cardiac monitoring, including an assessment of LVEF at baseline and during treatment, should be considered. In patients who develop relevant cardiac signs/symptoms during treatment, cardiac monitoring including LVEF assessment should be considered.

Patients experiencing corneal ulceration, Interstitial Lung Disease (ILD) or QTc prolongation with signs/symptoms of serious arrythmia will not be permitted to restart study treatment.

For the details, please refer to the local prescribing information.

7. Study Drug and Other Treatments

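### For toxicity unresolved after 3 weeks, the Section 6.7 text withdraws the patient from the study, while Table 3 and Section 3.9 only stop study drug

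*Protocol*

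**What the plan says.** Protocol Section 6.7 interrupts dosing for Grade 3 or unacceptable toxicity and then gives two rules in running text. The restart rule begins "If a toxicity resolves or reverts to ≤CTCAE grade 2 within 3 weeks of onset" and refers to Table 3 for the dose rules. The non-recovery rule says that if the toxicity is still above grade 2 after 3 weeks, "then the patient should be withdrawn from the study and observed until resolution of the toxicity".

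Table 3, in the same section, describes the non-recovery event as "Grade 3 or higher adverse reaction that does not improve to Grade 0-2 after withholding for up to 3 weeks", and its only instruction is to stop osimertinib permanently. Section 3.9 lists the same event among the situations for stopping study drug. It adds, for adverse events judged related, that one which "requires a dose hold of more than 21 days will result in permanent discontinuation of osimertinib". The section opens by saying that where treatment must be stopped, "this will not result in automatic withdrawal of the subject from the study", and that end-of-treatment and follow-up assessments go on.

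The QTc rule in Section 6.7 has the other consequence: without recovery in 21 days, "the patient will be permanently withdrawn from study treatment".

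The SAP does not address either rule. SAP Section 8.7.1 repeats the Protocol's inclusion of events up to 28 days after the last dose.

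**The concern.** Two instructions for one event cannot both be followed. Under one the patient leaves the study; under the other the patient stops the drug and stays in follow-up.

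Safety is this trial's only objective, and its primary outcome counts adverse events, serious adverse events, events of special interest and on-study deaths. The patients concerned are those with unresolved Grade 3 or higher toxicity, in whom complete follow-up matters most. If a site acts on the Section 6.7 sentence, new events late in the 28-day window may go unrecorded and the end-of-study call may not be made.

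Coding could also differ between sites. Section 6.3.3 records whether an adverse event caused withdrawal from the study, and SAP Section 8.1 tabulates dropouts with reasons. The same clinical course could be entered in two ways.

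**Working it through.** **1. The rules side by side**

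| Place in Protocol | When the 3 weeks start | What follows non-recovery |
|---|---|---|
| 6.7 text, restart sentence | onset of toxicity | not stated here |
| 6.7 text, non-recovery sentence | no starting point given | leaves the study, then observed |
| 6.7 Table 3 | withholding | osimertinib stopped permanently |
| 3.9, Grade 3 bullet | withholding | study drug stopped, follow-up continues |
| 3.9, related-event bullet | dose hold, more than 21 days | osimertinib stopped permanently |
| 6.7 QTc rule | 21 days, start not stated | withdrawn from treatment only |

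**2. Whether the wording has a defined meaning.** Section 3.9.1 explains withdrawal from the study as covering both study drug and assessments, and Section 3.10.1 uses the same gloss. The list in Section 3.10.1 headed "Reasons for withdrawal from the study" has four entries: eligibility not met, death, withdrawal of consent and loss to follow-up. Unresolved toxicity is not one of them.

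**3. What survives a literal reading.** Section 3.9.1 still has patients who leave early "complete the procedures described for End of Treatment Visit", no later than 7 days after study drug is discontinued. Observation until resolution is also required. However, under Section 6.3.2, follow-up after the last adverse event assessment in the study is no longer entered in the eCRF.

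**4. Days of the window at risk.** Inputs:

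- W = 28 days, the post-dose window (Protocol Table 1 and Section 8.5.1; SAP Section 8.7.1).
- h = 3 × 7 = 21 days, the hold at which failure is declared (Table 3). This assumes a full hold.
- e = days from that decision to the End-of-Treatment visit. I take 0 to 7, assuming the 7-day limit in Section 3.9.1 runs from the decision.

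Days at risk = W − h − e = 28 − 21 − e = 7 − e.

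- e = 0: 7 days, and 7/28 = 25% of the window.
- e = 7: 0 days.

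As an illustration, assume a hold from study day 43. The last dose is day 42, failure is declared on day 42 + 21 = 63, and the window closes on day 42 + 28 = 70. A visit on day 63 leaves 70 − 63 = 7 days uncovered. A visit on day 63 + 7 = 70 leaves none.

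The end-of-study call is a separate loss. Section 6.3.5 has the open adverse event question asked up to the last telephone contact, so the call would normally pick up events from any uncovered days.

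**5. The restart clock.** Take onset as day 0, the first withheld day as day g, and recovery to grade 2 or lower as day R. The Section 6.7 text allows restart if R ≤ 21. Table 3 allows it if R − g ≤ 21. They disagree for R = 22 to 21 + g. The documents give no value for g, so these are assumptions:

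- g = 0: no disagreement.
- g = 3: days 22 to 24.
- g = 7: days 22 to 28.

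**The case against.** The best defence is that the rest of the Protocol already settles the consequence. Section 3.9 keeps follow-up going. The Synopsis and Section 4 start the Follow-up Phase when study drug stops and end it only at 28 days after last dose, death, loss to follow-up, consent withdrawal or study end. Table 1 collects adverse events to 28 days after last dose. Many sites would probably do the right thing. That stands, and it limits the expected effect. It does not remove a sentence that tells the investigator something different at the point of managing toxicity.

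It is also fair that the triggering event has already been recorded, so the patient already counts as having an adverse event. Only new events or deaths in the last days could be missed. Section 6.3.2 lets the sponsor ask for more information on events still ongoing at the end of the study.

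On the clock, the defence is stronger. The natural onset is that of the Grade 3 toxicity that interrupts dosing, not of an earlier low-grade event. The restart sentence points to Table 3, and restart is optional. Dose modification is also referred to the local label, which is not among the documents. A delay between onset and hold is possible, since scheduled visits fall only on Day 1 of each 21-day cycle, but its length is unknown. The clock wording is therefore a secondary tidy-up.

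A reader might infer a loss longer than 7 days by counting the failure period from onset. The non-recovery sentence states no starting point, so the text does not support that. A reader might also infer a large effect on drug exposure by setting a patient who stops against one who restarts and completes six cycles. Those are different patients, one not recovering and one recovering. The SAP exposure formula, last date minus first date plus 1, would in any case count held days.

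**Conclusion.** The conflict over the consequence of non-recovery is real, and the Section 6.7 sentence is the one out of line. Its size is modest: 0 to 7 of the 28 post-dose days for new events, plus the end-of-study call, per affected patient. This rests on a literal reading of Section 6.7, a full 21-day hold, and an End-of-Treatment visit 0 to 7 days after the decision. The documents give no basis for estimating how many patients would be affected.

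The clock conflict is in the text but has no effect when dosing stops on the day of onset.

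Neither point changes the planned 60 patients, the confidence interval table, the safety analysis set, or the SAP summary that pools dose change, interruption and discontinuation. It is a low-priority correction, but it concerns the patients whose safety data matter most.

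**What to change.** Replace the non-recovery sentence in Section 6.7 with:

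> *Where toxicity has not come down to CTCAE grade 2 or lower within 3 weeks of the first day osimertinib is withheld, the patient permanently stops study drug, completes the end-of-treatment and follow-up assessments set out in Section 3.9, and is observed until the toxicity resolves.*

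As a secondary alignment, change the restart condition so that its 3 weeks also run from the first day osimertinib is withheld, matching Table 3 and Section 3.9.

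The cost is two sentences in a protocol amendment. If the change is judged substantial, Section 10.5 requires IRB approval and, where applicable, national regulatory approval, across 10 planned sites. No new data or visits are needed: dose interruptions and event start and stop dates are already recorded, and the End-of-Treatment visit and end-of-study call are already scheduled.

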Visit No.	1	2-7 (Day 1 of each cycle)	8	202
Study Days	-6 to 0	1-109 (21 day per cycle)	131	28 days post- EOT
Screening/Enrolment visit				
Informed consent ^(b)	Patients r	nust sign the informed conser procedures are p		study-specific
Eligibility Criteria	X			
Demographics/ Review medical history	X			
WHO Performance Status	X	X	X	
General Physical examination	X	Symptom-directed physical	examination only	
Concomitant medication recording	Continuous from time of ICF until 28 days after last osimertinib dose in treatment phase.			
Study Drug Administration				
Osimertinib dosing		The recommended dose is 80 mg osimertinib once a day until disease progression or unacceptable toxicity. Each cycle is of 21 days.		
Disease Evaluations (Disease char	racteristics wil	ll be performed as per routine	clinical practice)	
Baseline Disease Characteristics	X			
Safety Evaluations				
Physical examination	X	Symptom-directed physical examination only		
Vital parameters	X	X	X	
Adverse event monitoring		us from time of ICF until 28 days after last study osimertinib dose		
12-lead ECG	X	X	X	
Hematology & Biochemistry	X	X	X	

Footnotes:

- a. The Screening Phase begins when the first Screening procedure is conducted. Screening tests should be performed within 7 days of Cycle 1 Day 1 except for disease evaluations (performed as routine clinical practice).
- b. Must be signed before first study-related activity.

TABLE OF CONTENTS

PAGE

TITLE	PAGE	1
VERSIO	ON HISTORY	2
PROTO	COL SYNOPSIS	3
TIME A	AND EVENTS SCHEDULE	8
TABLE	OF CONTENTS	9
1.	Introduction	13
1.1	Background and rationale for conducting this study	13
1.2	Rationale for study design, doses and control groups	14
1.3	Benefit/risk and ethical assessment	14
1.4	Study Design	14
2.	Study Objectives	14
3.	Patient Selection, Enrolment, Randomisation, Restrictions, Discontinuation and Withdrawal	15
3.1	Inclusion criteria	15
3.2	Exclusion criteria	15
3.3	Patient enrolment and randomization	15
3.4	Procedures for handling incorrectly enrolled or patients	16
3.5	Methods for assigning treatment groups	16
3.6	Methods for ensuring blinding	16
3.7	Methods for unblinding	16
3.8	Restrictions	16
3.9 3.9.1	Discontinuation from study treatment Procedures for discontinuation of a patient from study drug	
3.10 3.10.1	Criteria for withdrawal	
3.11	Discontinuation of the study	18
4.	Study Plan and Timing of Procedures	19
5.	Study Assessments	20
5.1 5.1.1 5.1.2 5.1.3	Safety assessments Laboratory safety assessments Physical examination	21

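### For toxicity still above grade 2 after 3 weeks, Protocol Section 6.7 takes the patient out of the study, while Table 3 and Section 3.9 stop only osimertinib and keep follow-up going

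*Protocol*

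**What the plan says.** Protocol Section 6.7 interrupts dosing for a grade 3 or unacceptable toxicity. If the toxicity is not at grade 2 or lower after 3 weeks, "then the patient should be withdrawn from the study and observed until resolution of the toxicity". Table 3, directly below, gives the action for that event as "Permanently discontinue OSIMERTINIB" and says nothing about leaving the study.

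Section 3.9 covers stopping study drug. Its list of reasons includes "Grade 3 or higher adverse reaction that does not improve to Grade 0-2 after withholding for up to 3 weeks". It says of stopping treatment that "this will not result in automatic withdrawal of the subject from the study", and that "end-of-treatment assessments should be obtained and scheduled follow-up phase assessments should continued" as set out in the schedule.

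The protocol gives the two terms different meanings. Sections 3.9.1 and 3.10.1 both explain leaving the study as giving up study drug and assessments together. Section 3.10.1, under "Reasons for withdrawal from the study", lists ineligibility, death, withdrawn consent and loss to follow-up, but not toxicity. The list is not stated to be exhaustive.

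On follow-up, Table 1 runs adverse event monitoring "until 28 days after last study osimertinib dose". Protocol Section 4 and SAP Section 5.2 name the events that end follow-up, and toxicity is not one of them. Protocol Section 8.5.1 and SAP Section 8.7.1 include events within 28 days of the last dose in the summaries.

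**The concern.** One event has two incompatible instructions. Under Section 3.9 the patient stops osimertinib, has the end-of-treatment visit, and is followed for adverse events to day 28 and to the end-of-study call. Under Section 6.7, read with the protocol's own meaning of study withdrawal, assessments end. No clause says which section prevails.

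Safety is the trial's only objective, and the patients concerned have persistent severe toxicity. If a site closes such a patient out early, a new adverse event, serious event or death in the remaining days may never be recorded. The patient stays in the safety analysis set (SAP Section 5.4) and missing events are not imputed (SAP Section 7.3). The denominator is therefore unchanged while the numerator can only fall.

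Observing the patient until the toxicity resolves does not close this gap. It concerns the toxicity already known, and does not mention new events, the eCRF or the end-of-study call. Section 6.3.2 also lets events unresolved at the last adverse event assessment be followed without further eCRF recording.

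**Working it through.** **Text comparison, same trigger (not at grade 2 or lower after 3 weeks)**

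| Place | Action | Follow-up |
|---|---|---|
| Protocol 6.7, text | leave the study | observe the toxicity only |
| Protocol 6.7, Table 3 | stop osimertinib | not mentioned |
| Protocol 3.9 | stop study drug | end-of-treatment and follow-up continue |
| Protocol 6.7, QTc paragraph (parallel case, 21 days) | stop study treatment | not mentioned |
| Protocol 6.3.1, Table 1, Section 4; SAP 5.2 | – | continues to 28 days after last dose or end of study |

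The Section 6.7 text is the only outlier, and it differs from the QTc paragraph of its own section. The likely intent was withdrawal from study treatment.

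**Post-dose days at risk**

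Inputs: 28-day window (Protocol 8.5.1, SAP 8.7.1); decision at 3 weeks = 21 days (6.7); end-of-treatment procedures "not later than 7 days after discontinuation of study drug" (3.9.1); end-of-study call 28 days after the end-of-treatment visit (Section 4).

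- Dosing stopped at onset: 28 − 21 = 7 days remain at the decision, and 7/28 = 25%.
- End-of-treatment visit 0 to 7 days after the decision: day 21 to 28 after last dose, so 7 to 0 days remain after it. The end-of-study call would fall on day 21 + 28 = 49 to 28 + 28 = 56.
- Dosing stopped k days after onset, with the 3 weeks counted from onset: 28 − (21 − k) = 7 + k days remain. The documents give no k. Assuming k = 0 to 7, the range is 7 to 14 days. Table 3 counts from withholding, which gives 7.

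**Effect on the summaries (n = 60)**

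- One missed patient in a row: 1/60 = 1.67 percentage points at most.
- SAP 8.7.1 has 11 rows in its overall summary. A drug-related, non-serious, grade 3 or higher index event that stops dosing already fills 7: AEs; TEAEs; grade 3+; grade 3+ related; treatment-related; leading to a dosing change or stop; and the related version of that last row.
- 11 − 7 = 4 rows can still move: serious, treatment-related serious, fatal and related fatal. If the related index event was itself serious, only the 2 fatal rows can. The missed event's own system organ class and preferred term rows can also move.
- This assumes that events in the 28-day window enter the TEAE rows.

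**Illustration with exact (Clopper-Pearson) limits**

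Lower limit = Beta quantile (0.025; x, n − x + 1); upper limit = Beta quantile (0.975; x + 1, n − x).

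- Plan's own 5% row (Protocol 8.2, SAP 4): x = 3, n = 60 gives 5.00%, limits 1.04 to 13.92. This reproduces the printed 1.0 and 13.9.
- With one serious event missed: x = 2, n = 60 gives 3.33%, limits 0.41 to 11.53.

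**The case against.** The strongest reply is that this is a one-phrase slip that the rest of the protocol already corrects. Section 3.9 lists the trigger in the same words as Table 3. Section 4 sends anyone who stops for a Section 3.9 reason to the end-of-treatment visit and then the call. Section 3.9.1 keeps the end-of-treatment procedures even for those leaving the study early, and Section 6.4 requires every serious event to be reported. Harm therefore needs a site to set several provisions aside and to miss a new event in a patient it is already watching. Other wording is loose too: Section 3.9 says follow-up should continue rather than must, and Section 6.3.3 has a field for an adverse event that led to study withdrawal, so such withdrawal is contemplated.

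Much of this stands on size. Few days are at risk, the index event is already counted, and no hypothesis is tested. ILD, corneal ulceration and QTc events have their own treatment-discontinuation rules. The 3/60 example is illustrative, and its two intervals largely overlap.

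It does not remove the conflict. Section 6.7 also says should, so neither instruction outranks the other. The Section 6.3.3 field makes the inconsistency visible in the data: for the same event, a site following Section 6.7 would answer yes and one following Section 3.9 would answer no. A site managing a severe toxicity is likely to consult Section 6.7.

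**Conclusion.** The Section 6.7 sentence is wrong as written and should be corrected. The contradiction is certain from the text. Its effect on the reported rates can only be downward and is probably small: in the base case 7 of 28 post-dose days, or none after a late end-of-treatment visit, and at most 1.7 percentage points per affected patient per row.

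The size rests on dosing having stopped at onset (7 + k days otherwise, with k assumed), on 60 patients in the safety set, and on the index event being drug-related for the row count. The total effect cannot be computed because the documents do not give the expected number of affected patients.

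**What to change.** In Protocol Section 6.7, replace withdrawal from the study with permanent discontinuation of study treatment, keeping the instruction to observe the patient until the toxicity resolves. Add that, unless the patient withdraws consent, the end-of-treatment visit, eCRF recording of all adverse and serious adverse events to 28 days after the last dose, and the end-of-study contact continue as Section 3.9 and Table 1 provide.

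The cost is one sentence of protocol wording. The follow-up is already scheduled, so no visits are added.

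### The Section 6.7 bullet on later dose interruptions omits the grade and QTc restart conditions of Table 3, so read literally the two conflict

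*Protocol*

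**What the plan says.** Several places in the protocol govern what happens after a dose hold.

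- **Section 6.7, opening text.** Dosing is interrupted for grade 3 and/or unacceptable toxicity. "If a toxicity resolves or reverts to ≤CTCAE grade 2 within 3 weeks of onset, treatment with study drug may be restarted" at 80 mg or 40 mg under the rules of Table 3, with the sponsor's study physician agreeing as needed.
- **Table 3, general rows.** "If Grade 3 or higher adverse reaction improves to Grade 0-2 after withholding of OSIMERTINIB for up to 3 weeks", either strength may be used at restart. For a "Grade 3 or higher adverse reaction that does not improve to Grade 0-2 after withholding for up to 3 weeks", the drug is permanently discontinued.
- **Table 3 and the QTc paragraph of Section 6.7.** After QTc above 500 msec, the drug is held until QTc is below 481 msec or back to a high baseline, "and then restarted at a reduced dose of 40 mg". The QTc paragraph adds permanent withdrawal from treatment if the event has not come down to grade 1 or lower within 21 days.
- **Section 3.9.** It repeats the Grade 0-2 criterion among the reasons for stopping study drug and adds: "Any adverse event deemed to be related to osimertinib that requires a dose hold of more than 21 days will result in permanent discontinuation". On QTc it lists only prolongation with serious arrhythmia. It gives no QTc restart threshold or dose.
- **Bullet after Table 3.** Under the lead-in "On resolution of toxicity within 3 weeks" stands one bullet: "If an AE subsequently requires dose interruption, study drug may restart at the same dose or the reduced dose, on resolution/improvement of the AE". Its closing words leave the restart to the investigator: "on resolution/improvement of the AE at the discretion of the Investigator".

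**The concern.** The word subsequently marks the bullet as the rule for a repeat interruption. It accepts improvement without saying to what grade, and it offers the same dose without setting QTc events apart. The conditions in the opening text, Table 3, the QTc paragraph and Section 3.9 are not confined to a first episode, and nothing makes the bullet subject to them. Two rules therefore reach the same patient.

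Safety is at stake first. The patients concerned have repeated toxicity, and investigators at the 10 planned sites could handle like cases differently while each followed a line of the protocol. The data come second. Whether a patient restarts fixes the date of last dose. That date feeds exposure (SAP Section 8.5), the end of the 28-day adverse-event window (SAP Section 8.7.1) and the reason for discontinuation in the disposition table (SAP Section 8.1).

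**Working it through.** No figure in the plan depends on this rule, so the check sets the passages side by side. Each row is an event that leads to a **later** interruption.

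| Later event | Bullet, read literally | Table 3, QTc paragraph, Section 3.9 | Result |
|---|---|---|---|
| Grade 3 or higher, down to Grade 0-2 within 21 days | may restart | may restart | no conflict |
| Grade 4, improved to Grade 3 at day 14 | may restart | keep withholding | conflict |
| Grade 4, still Grade 3 at day 21 | may restart | permanent stop | conflict |
| Drug-related, held 28 days | depends on the lead-in | permanent stop (Section 3.9) | ambiguous |
| QTc above 500 msec, no arrhythmia, recovered in time, patient on 80 mg | same or reduced dose | reduced dose only | conflict on dose only |
| QTc above 500 msec, improved but not recovered by 21 days | may restart | permanent withdrawal (QTc paragraph) | conflict |
| Event below Grade 3, other than QTc | may restart | Grade 0-2 rows do not apply | no conflict on grade |
| Interstitial lung disease, corneal ulceration, QTc with serious arrhythmia | not excepted | restart barred at the end of Section 6.7 | settled by the explicit bar |

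**The lead-in can be read in two ways.**

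1. It describes the earlier toxicity, which has resolved in time. The bullet then sets no limit on the later hold, and the 28-day row conflicts with Section 3.9.
2. It governs the later event. A 28-day hold then falls outside the bullet, and there is no conflict on time. The lead-in still names no grade and no QTc dose. It also speaks of resolution where the bullet accepts improvement, so the grade required remains unstated.

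The grade and QTc conditions are therefore missing from the bullet on either reading. Only the time limit turns on the choice.

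**Size.**

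- One patient in the disposition table: 1/60 = 1.7 percentage points.
- Exposure under the SAP formula (last date − first date + 1), for a patient whose last dose before the hold is at the end of Cycle 3, Day 3 × 21 = 63. If stopped for good: 63 − 1 + 1 = 63 days. If restarted and treated to the end of Cycle 6, Day 6 × 21 = 126: 126 − 1 + 1 = 126 days. The difference is 63 days, hold days included, because the formula does not subtract them.
- The 28-day window for that patient closes on Day 63 + 28 = 91 or Day 126 + 28 = 154.
- Number of patients: not in the documents. As an assumption, if 2% to 10% of 60 patients had any second interruption, that is 1.2 to 6, or about 1 to 6 patients. Only those in a conflicting row would be handled differently, so this range is a ceiling, not an estimate.
- The SAP Section 8.7.1 row for events leading to a change, interruption or discontinuation of dosing pools all three. A patient whose drug was interrupted is already in it, so it does not move.

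**The case against.** The strongest reply is that the rules can be read together. The bullet is permissive and does not claim to replace Table 3. The stopping rules are worded more firmly: Table 3 instructs permanent discontinuation, and the 21-day entry in Section 3.9 and the QTc paragraph are both mandatory. If they cover every episode, they cover later ones too, and a careful investigator would apply them. The bullet also has a harmless use. Section 6.7 allows interruption for unacceptable toxicity that need not be Grade 3; Grade 0-2 is then no test, and restart on improvement at discretion makes sense. Finally, the protocol sends dose modification to the locally approved prescribing information, which is not among the documents and may narrow what sites do in practice.

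Much of this stands. Divergent practice is possible, not inevitable, and the sharp outcome of restart against permanent stop belongs to a narrow set of cases. What remains is that the bullet is not limited to events below Grade 3, carries no cross-reference and makes no QTc exception. The explicit bar at the end of Section 6.7 covers none of the conflicting rows. A site that follows the bullet as written could restart a patient whom Table 3 stops.

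**Conclusion.** The point holds as a conflict of wording on two conditions: the Grade 0-2 requirement for Grade 3 or higher reactions (Table 3, Section 3.9), and the QTc threshold and restart dose (Table 3 and the QTc paragraph of Section 6.7). It is worth correcting for patient safety and consistency between sites. The effect on disposition, exposure and the 28-day window is probably small and cannot be estimated from the documents.

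A reader might infer more than the documents support:

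- **That the bullet overrides the 3-week limit.** This depends on which toxicity the lead-in governs, and the text does not settle it.
- **That the stricter conditions cover any interruption.** The Grade 0-2 rows concern Grade 3 or higher reactions, and the 21-day entry in Section 3.9 concerns events judged related to osimertinib.
- **That every conflict means restart against permanent stop.** A later QTc event that recovers in time differs only in dose.
- **That Section 3.9 contradicts the bullet on QTc restart.** It contains no QTc restart condition.
- **That the planned adverse-event tables would shift through reclassified discontinuations.** The pooled row would not.

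The conclusion rests on a literal reading of the bullet and on the absence of any first-episode limit in the other passages. It takes no view on which clinical rule or dose is right.

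**What to change.** Reconcile the bullet and its lead-in with the opening text of Section 6.7, Table 3, the QTc paragraph and Section 3.9, so that one consistent set of restart conditions is stated, or cross-referenced, for later interruptions. The revised text should make clear which toxicity the 3-week lead-in refers to. The sponsor's clinical team decides the content.

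The cost is one protocol wording change and a note to sites. It needs no new data, no extra procedures and no change to the SAP.
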